Azithromycin is *pregnancy category B* – animal studies using maternally toxic doses showed no fetal harm. Limited studies suggest azithromycin is excreted in human milk in a sustained fashion.³⁴ There are no specific drug-drug interactions warranting dose adjustments when given with other medications. Elimination is by both hepatic and renal route, and no specific adjustments are mandated for patients with renal or hepatic insufficiency. The long elimination 1/2-life of 68 hours is due to extensive uptake and subsequent release of drugs from tissues. The only absolute contraindications are rare: known hypersensitivity reaction to azithromycin, erythromycin or other macrolide antibiotic or history of

cholestatic jaundice due to azithromycin. Potential adverse events include very rare (<1%) allergic hypersensitivity (mild and severe skin reactions – Stevens Johnson Syndrome and toxic epidermal necrolysis, angioedema and anaphylaxis) and clostridium difficile-associated diarrhea. With multi-day azithromycin therapy, 0.6% of patients discontinued azithromycin due to side effects. With single 1-2 gram doses, gastrointestinal symptoms (nausea 5-18%, diarrhea/loose stools 7-14%, abdominal pain 5-7%, vomiting 2-7%, and dyspepsia 1%) as well as vaginitis 2% and dizziness (1%) were the most commonly reported side effects. No other side effect occurred with a frequency greater than 1%.

Azithromycin has been associated with hypertrophic pyloric stenosis in some observational studies. In a retrospective study, oral azithromycin exposure during the first 14 days after birth was associated with an increased incidence of pyloric stenosis.³⁵ However, an increased risk of pyloric stenosis was not reported in infants following a single dose of azithromycin to women in labor in randomized trials in the US and Gambia.^{13-14, 16} The much larger sample size of the proposed study affords the opportunity to further explore this question.

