4.1 Data Forms

The following forms will be used for this study:

Form Name	Purpose	Key Data Elements	Data Source
Contact and Scheduling Form	To facilitate participant follow-up by documenting contact information and projected study visit schedule	Contact information, date of enrollment, date of follow-up visits	Participant interview, study calendar
Screening and Enrollment Form	To determine eligibility and record consent status	Screening date, review and confirmation of inclusion/exclusion criteria, consent status/date.	Participant interview/report, clinical assessment, provider report, medical records
Randomization Form	To confirm eligibility and track randomization	Eligibility confirmation, randomization date/time, drug administration date/time, any problems with drug administration (e.g., vomiting, dropped med, etc).	Study records, participant interview and observation

Form Name	Purpose	Key Data Elements	Data Source
Maternal Baseline Data Form	To collect additional maternal information	
 Demographic and baseline clinical data: admission date/time, EDD, GA, age, height, weight, pregnancy and medical history, etc. Events during labor and delivery: timing of onset of labor, prolonged labor, premature rupture of membranes, date/time/type of membrane rupture, date/time/type of delivery, indication for induction (if applicable), vital signs during labor (temp, HR, RR, BP), complications, etc. Events after delivery: complications, vital signs, etc. Infection assessment pre- and post-delivery Antibiotic treatment pre- and post-delivery Discharge information 	Participant interview/report, provider report, medical records
Neonatal Baseline Data Form	To collect information about the infant directly after delivery.	
 Sex Birthweight Delivery outcome (live or stillbirth) Complications Infection assessment Discharge information: date/time, status (discharged, transferred, died) 	Participant interview/report, provider report, medical records
Maternal and Neonatal Follow-up Form	To collect maternal and infant health status during follow-up visits at 3 days, 7 days and 42 days after delivery.	
 Timing follow-up Maternal and infant status since discharge: general status, symptoms, indication of infection, clinic visits, hospitalizations, antibiotic use Temperature 	In-person participant interview/report and clinical exam

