 - Time from drug administration until initial discharge after delivery (time may vary by site).
 - Maternal readmission within 42 days of delivery.
 - Maternal admission to special care units.
 - Maternal unscheduled visit for care.
 - Maternal GI symptoms including nausea, vomiting, and diarrhea and other reported side effects.
 - Maternal death due to sepsis using the Global Network algorithm of causes of death.
- Other Neonatal Outcomes
 - Other neonatal infections (e.g. eye infection, skin infection, omphalitis, urinary tract infection, respiratory rate ≥ 60 breaths/minute)

- Neonatal initial hospital length of stay, defined as time of delivery until initial discharge (time may vary by site).
- Neonatal readmission within 42 days of delivery.
- Neonatal admission to special care units.
- Neonatal unscheduled visit for care.
- Neonatal death due to sepsis using the Global Network algorithm for causes of death.
- Pyloric stenosis within 42 days of delivery, defined as clinical suspicion based on severe vomiting leading to death, surgical intervention (pyloromyotomy) as verified from medical records, or radiological confirmation.

Detailed definitions for deriving the associated variables are included in Section 9.

Type of culture positive infections, antimicrobial resistance and maternal and infant microbiome diversity were compared in an ancillary study and the associated analyses described in a separate analysis plan.

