Maternal GI symptoms including nausea, vomiting, and diarrhea and other reported side effects.	Binary	
The outcome will be defined as “Yes” if vomiting or diarrhea are reported after delivery on AZ03 or AZ05a; an unscheduled care visit for nausea, vomiting, or diarrhea is reported on AZ05a; or an unscheduled care visit for nausea, vomiting and/or diarrhea is reported on AZ07; or a mechanistically-related AE is reported (e.g. abdominal pain); and “No” otherwise. The outcome will only be missing for mothers that are lost to follow-up prior to completion of a Day 7 visit and had no symptoms or side effects reported prior to becoming LTF.
 
Analysis population(s): As Treated

Neonatal Other Infections	Binary	
The event will be defined as “Yes” if any infection is reported that does not qualify for sepsis prior to day 28 and “No” otherwise. Other neonatal infections include eye infection with swelling and drainage, skin infection with 10 or more pustules or bullae, omphalitis, urinary tract infection, pyelonephritis or kidney infection, pneumonia or lung infection, meningitis, other infection documented in clinical record or respiratory rate ≥ 60. The outcome will only be missing for infants that are lost to follow-up prior to completion of a Day 7 visit and neonatal deaths prior to 7 days that do not qualify for sepsis or other infections.
 
Analysis population(s): ITT (all-comer and high risk)

Variable	Type	Definition
Neonatal initial hospital length of stay	Ordinal	Defined as the date/time of initial discharge reported on AZ04 or AZ08 – date/time of delivery reported on AZ03 Analysis population(s): ITT (all-comer and high risk)
Neonatal readmissions within 42 days of delivery	Binary	Only defined for live births who were initially discharged from the hospital following delivery as documented on AZ04 or AZ08 (i.e. stillbirths or infants that die during the initial hospitalization for delivery will be excluded from the numerator and denominator). The outcome will be defined as “Yes” if the location of any subsequent study visit on AZ05b is In-patient (hospitalized), or if there is an AZ08 form where the infant is noted as admitted or has a non-missing admission date; and “No” otherwise. The outcome will only be missing for infants that are lost to follow-up prior to completion of a Day 7 visit and had no readmission reported prior to becoming LTF. Analysis population(s): ITT (all-comer and high risk)

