9.5 Secondary Outcome Analyses

Binary secondary outcomes (e.g. individual components of the primary outcome, all other infection indicators, use of antibiotics, maternal and neonatal readmission as well as admission special care unit, maternal GI symptoms, and pyloric stenosis) will be analyzed in a similar manner to the primary analysis of the primary outcomes. Models will be focused on providing estimates of relative risk and associated confidence intervals as opposed to being used for formal tests of hypothesis. If regional differences are observed for the primary outcome, then region-specific models for all secondary outcomes will be run in order to get region-specific estimates of relative risk.

For secondary publications, secondary outcomes may also be explored using additional exploratory models including individually: 1) a treatment by site interaction term, 2) any other antibiotic use during labor (yes or no) and its interaction with treatment, and 3) mode of delivery (cesarean or vaginal) and its interaction with treatment. If the interaction term for any of these models has a $p < 0.1$, then effects will also be reported by the relevant subgroups. These exploratory secondary models will also include any demographic or clinical variables found to differ significantly between the treatment arms in the preliminary analyses described above. From each final model, adjusted relative risk estimates for treatment will be obtained.

For the outcome of time from drug administration until initial discharge after delivery and the outcome of neonatal initial hospital length of stay, the same analysis steps will be employed but using models appropriate for the distribution of these variables (Brock 2011). Specifically, Kaplan-Meier survival curves will be fit to the data in order to get cumulative incidence curves by treatment group of hospital discharge, obtained by treating in-hospital mortality as a competing risk.

10. SAFETY ANALYSIS:

No formal safety analyses are planned as a part of this study, although SAEs and side effects will be summarized. No formal hypothesis tests will be conducted, but descriptive p-values generated using Cochran-Mantel-Haenszel statistics with stratification by GN site will be generated.

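### The maternal GI side-effect outcome has no stated end day and no early-window version, so background illness up to about day 42 can pull its relative risk toward 1.

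*Combined protocol and SAP*

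**What the plan says.** SAP 3.2 names the outcome, "Maternal GI symptoms including nausea, vomiting, and diarrhea and other reported side effects", without a time frame and points elsewhere for the derivation: "Detailed definitions for deriving the associated variables are included in Section 9".

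SAP 9.2 holds the working definition. A woman is positive "if vomiting or diarrhea are reported after delivery on AZ03 or AZ05a; an unscheduled care visit for nausea, vomiting, or diarrhea is reported on AZ05a". She is also positive when AZ07 records unplanned care for these symptoms. The last route reads: "or a mechanistically-related AE is reported (e.g. abdominal pain); and “No” otherwise". No last day is given for any of these routes. Day 7 appears only in the missing-data rule, where it decides who has a missing value and not which events count. The analysis population is As Treated.

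The timing of the forms comes from other sections. The maternal readmission row of SAP 9.2 treats AZ05a as the study-visit form. Protocol 4.1 describes a follow-up form for the visits at days 3, 7 and 42, with content that includes "Maternal and infant status since discharge: general status, symptoms, indication of infection". Protocol 2.4.7 says side effects are sought at all three visits, and Appendix 3 marks drug side effects at day 42.

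SAP 9.5 includes maternal GI symptoms among the binary secondary outcomes and says of their analysis: "Models will be focused on providing estimates of relative risk and associated confidence intervals".

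**The concern.** The exposure is one oral dose in labor, and Protocol 1.6.3 lists gastrointestinal symptoms among its most commonly reported side effects. The outcome meant to measure them gathers everything reported over about six weeks. Some late episodes will be ordinary illness unrelated to the dose, and they enter both arms. A relative risk is sensitive to this: adding the same background to numerator and denominator moves it toward 1. For a harm outcome, that makes the drug look better tolerated than it is. The SAP plans no attribution rule, early window or split by visit that would let a reader separate the two periods.

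**Working it through.** **Step 1: is there an end day anywhere?**

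| Place | Time limit for GI symptoms |
|---|---|
| SAP 3.2, outcome list | None; defers to SAP 9 |
| SAP 9.2, GI symptoms row | Vomiting or diarrhea counts after delivery; no end |
| SAP 9.2, opening rule | Infections, antibiotic use and medical care count to the end of the relevant visit window; no window is named for this outcome |
| Protocol 2.6(i) | None |
| Protocol 2.8 | Surveillance in labor and postpartum; no end |
| Protocol 2.4.7, 4.1 and Appendix 3 | Last visit at day 42 |

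No end is written, and the practical limit is the end of follow-up at about day 42. By contrast, the SAP 9.2 row for maternal antibiotic use states day 42.

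**Step 2: is observation time the same for every woman?** Under the missing-data rule, a symptom-free woman lost after completing her Day 7 visit is scored negative. Women observed for about 7 days and for 42 days are therefore pooled in one binary variable.

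**Step 3: how much drug is left late on?** Protocol 1.6.3 states: "The long elimination 1/2-life of 68 hours is due to extensive uptake". The fraction remaining after t hours is 0.5^(t/68).

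- Day 7: 0.5^(168/68) = 0.18
- Day 14: 0.5^(336/68) = 0.03
- Day 42: 0.5^(1008/68) is below 0.001

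This makes a direct drug effect less plausible in the later weeks. It does not mark a sharp boundary at day 7.

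**Step 4: effect on the relative risk.** The documents give no figure to reproduce. Protocol 1.6.3 gives rates after single 1-2 g doses (nausea 5-18%, diarrhea 7-14%, abdominal pain 5-7%, vomiting 2-7%), but no placebo or background rates. Everything below is assumed.

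Let p be the early risk in an arm and b an independent late background risk, equal in both arms. The observed risk is 1 - (1 - p)(1 - b) = p + (1 - p)b.

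With p = 8% on azithromycin and 3% on placebo:

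- RR = (0.08 + 0.92b) / (0.03 + 0.97b)
- RD = (0.08 - 0.03)(1 - b)

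| b | Azithromycin | Placebo | RR | RD (points) |
|---|---|---|---|---|
| 0 | 8.00% | 3.00% | 2.67 | 5.00 |
| 2% | 9.84% | 4.94% | 1.99 | 4.90 |
| 5% | 12.60% | 7.85% | 1.61 | 4.75 |
| 10% | 17.20% | 12.70% | 1.35 | 4.50 |

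A second assumed pair, 10% vs 5%, behaves alike. Its RR of 2.00 becomes 1.71, 1.49, 1.31 and 1.17 for b = 2%, 5%, 10% and 20%, and its RD of 5.0 becomes 4.9, 4.75, 4.5 and 4.0 points.

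**Step 5: unequal background.** Suppose late risk were 8% on azithromycin and 10% on placebo, with early risks of 10% and 5%. The observed risks are 1 - 0.90 × 0.92 = 17.2% and 1 - 0.95 × 0.90 = 14.5%, so RR = 1.19 and RD = 2.7 points. The risk difference is protected only while background is about equal.

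**The case against.** Several objections stand and limit the point.

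- A reader might infer that events can accrue without limit. They cannot: follow-up closes the window near day 42. What is missing is the written end and any view of the early period.
- A reader might infer that this outcome is the odd one out. It is not: in SAP 9.2 the rows for special care admission and unscheduled visits also state no last day. The gap matters more here because this outcome is read as a side effect of one dose.
- The recall period is not certain. Protocol 4.1 summarizes the follow-up form without its number, so the link to AZ05a is inferred, and the exact day-42 question cannot be seen.
- The absolute excess is not hidden. SAP 7.1 provides for percentages by arm, SAP 10 summarizes side effects with descriptive p-values, and the risk difference moves little under equal background.
- A reader might take the half-life as proof that everything after day 7 is background. It is not: about 18% of the drug remains at day 7. Protocol 1.6.3 also lists *Clostridium difficile*-associated diarrhea as a possible adverse event, which is a reason to keep the longer window.

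None of this supplies an early estimate. The plan, followed as written, yields one relative risk that mixes early and late events.

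**Conclusion.** The point holds as a modest improvement to a safety summary. SAP 9.2 counts GI symptoms to about day 42 with no stated end and no attribution rule, and any shared late background pulls the planned relative risk toward 1. The direction follows from the arithmetic, given background that is independent of the early risk and equal in both arms. The size does not follow from the documents. The fall from 2.67 to between 1.99 and 1.35 rests on assumed early risks of 8% and 3% and assumed background of 2% to 10%.

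A reader might conclude that the trial will materially understate harm, or that its conclusions are at risk. The documents do not support either reading. The risk difference is nearly unchanged under equal background, percentages by arm will be available, and the outcome is secondary, As Treated and descriptive. No primary inference depends on it.

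**What to change.** In the GI symptoms row of SAP 9.2:

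1. State day 42 as the end of the window for the existing outcome.
2. Add a pre-specified early version limited to symptoms reported through the Day 7 visit: AZ03, the Day 3 and Day 7 AZ05a, and unscheduled care or adverse events dated by then. Day 7 is an existing visit and already the cut-off in the missing-data rule.
3. Report both versions side by side in the As Treated population, so that late antibiotic-associated diarrhea stays visible.
4. Give the risk difference with its confidence interval beside the relative risk for each.

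The cost is SAP wording, one extra derived variable and two estimates to report instead of one. No new data collection is needed.

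This does not change the start of the window. The definition counts vomiting or diarrhea only from delivery onward, although the dose is given in labor. That is a separate issue.

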4. STUDY METHODS

[figure not shown]
4.1 Overall Study Design

This study was a masked, placebo-controlled RCT of pregnant women laboring in health facilities of the eight Global Network sites/other health facilities. The investigational regimen is 2 g of azithromycin and the comparison arm is an identical placebo which is given orally. Both groups received the standard of care during labor, delivery and postpartum per local standards.

Women were followed up until discharge and surveillance maintained (in-person), with visits at 3-day, 7-day and 42-day postpartum to identify maternal or infant infection, unexpected medical visits, side effects, and other study outcomes. Supplemental phone contacts will be conducted at 14-day and 28-day postpartum to review maternal and neonatal signs of infection using WHO criteria. If signs of infection are identified during the review, participants will be asked to visit a study facility for further assessment. These supplemental contacts will reinforce the participants' ability to self-assess for signs of maternal and neonatal infection and improve identification of infection between the 7-day and 42-day postpartum visits. If phone contact is not feasible, in-person visits may be conducted.

A study schematic is shown below

Study Schematic

4.2 Study Population

Pregnant women laboring in health facilities of the eight Global Network sites/other health facilities were eligible. Health facilities may include any hospitals and health centers where women routinely deliver within the study sites.

Inclusion Criteria

- Pregnant women in labor ≥ 28 weeks GA (by best estimate) with a pregnancy with one or more live fetuses who plan to deliver vaginally in a facility.
- Admitted to health facility with clear plan for spontaneous or induced delivery.
- Live fetus must be confirmed via presence of a fetal heart rate prior to randomization.
- ≥ 18 years of age or minors 14-17 years of age in countries where married or pregnant minors (or their authorized representatives) are legally permitted to give consent.

- Have provided written informed consent [Note: written informed consent may be obtained during antenatal care, but verbal re-confirmation may be needed (per local regulations) at the time of randomization].

Exclusion Criteria

- Non-emancipated minors (as per local regulations)
- Evidence of chorioamnionitis or other infection requiring antibiotic therapy at time of eligibility (however, women given single prophylactic antibiotics with no plans to continue after delivery should not be excluded).
- Arrhythmia or known history of cardiomyopathy.
- Allergy to azithromycin or other macrolides that is self-reported or documented in the medical record.
- Any use of azithromycin, erythromycin, or other macrolide in the 3 days or less prior to randomization.
- Plan for cesarean delivery prior to randomization.
- Preterm labor undergoing management with no immediate plan to proceed to delivery.
- Advanced stage of labor (>6 cm or 10 cm cervical dilation per local standards) and pushing **or** too distressed to understand, confirm, or give informed consent regardless of cervical dilation.
- Are not capable of giving consent due to other health problems such as obstetric emergencies (for example, antepartum haemorrhage) or mental disorder.
- Any other medical conditions that may be considered a contraindication per the judgment of the site investigator.
- Previous randomization in the trial.

4.3 Study Arm Assignment and Randomization

Randomization of participants was carried out to obtain a 1:1 allocation ratio between the treatment and placebo arms. Randomization was stratified by site. A computer algorithm generated by the data coordinating center (DCC) created the random assignment to one of the treatment arms based on randomly permuted block design with randomly varied block sizes. The block sizes were known only by the DCC personnel. Each site received a lot of the study drug to be distributed sequentially at the participating health facilities which are randomizing women for the study site.

4.4 Masking and Data Lock

Both the azithromycin and placebo were procured from the same manufacturer. The packaging was standardized across sites and will be labeled as: "Azithromycin 2 g or Placebo", with the expiration data and a unique identifier. A certificate of authenticity was provided.

Clinical and research staff involved with participant follow-up and/or clinical care as well as the women were masked to treatment status unless there was a serious adverse event potentially related to the treatment modality that required unmasking for safety reasons. There was one individual identified at each site for the role of pharmacist who monitored randomization, drug supply, and safety. Under the instruction of the DCC, the study pharmacist was trained and

authorized to apply un-masking procedures, if concerns about randomization or participant safety were identified.

Data Lock: Most data were to be entered real time into a tablet-based electronic data capture system with paper forms provided as back up if needed. Some delay in entry was anticipated for data obtained from records of readmissions/hospitalizations and unexpected visits for clinical care.

At the end of the study, data were locked at the site level with final analysis data sets generated and locked once data from all sites have been received and all queries processed. For each site, data collection for the protocol was stopped approximately 42 days after the last pregnant woman was randomized into the study at that site. Site will transmit all final data to the central database at the DCC within one month of this date, and data will be locked within two to four months post last follow-up visit.

The outcomes of occurrence of infectious diseases and of pyloric stenosis will be determined programmatically where possible. Any remaining cases will go through an adjudication process for final outcome determination. The details of the adjudication process and the programmatic algorithm for determining endpoints or routing the cases for review are detailed in a separate adjudication plan.

A single interim analysis is planned for this study. A data snapshot will be taken for that interim analysis. Resolution of queries on and adjudication of data required for the interim analysis will be a focus prior to the snapshot but timely completion of the interim analysis will be prioritized over resolving all outstanding data issues. The details and timeline of the interim analyses are described in section 11. For the interim analysis, only a senior statistician and the study statistician at the DCC and the Data Monitoring Committee (DMC) will be unmasked to analysis results.

Otherwise, the study will not be unmasked until after study completion or early termination and subsequent data lock.

